6.4. Visit 5: Day 7 (± 24 hours)

Visit 5 assessments may be performed in clinic, in hospital, or at the subject's home by the study coordinator or designee, or a home nursing vendor.

- Nasal samples (2 total, 1 from each nostril)

- Vital signs, including O₂ saturation (unless conducted as a home visit)
- Assessment of AEs, concomitant medications, hospitalizations, re-hospitalizations, ICU admissions or utilization of ICU care > 24 hours, standard of care test results (ie, chest radiographs, microbiology, echocardiograms), mechanical ventilation (invasive and non-invasive of any duration), and supplemental O₂ use (≥ 2 L/min for >24 hours). Review of procedure-related AEs only, if home visit.

6.5. Visits 6-8: Days 9, 13, and 17 (± 24 hours)

Visit 6-8 assessments must be performed in clinic or in hospital and should be performed in the following order and documented at these visits (also refer to [Appendix 2](#), Study Procedures Table):

- FLU-PRO questionnaire (Day 9 only)
- Vital Signs (body temperature, heart rate, respiratory rate, and blood pressure)
- O₂ saturation (on room air)
- Weight
- Pre-dose blood draw for central and local laboratory analysis:
 - Safety Labs (hematology and serum chemistry to include to include WBC with differential, Hgb, platelets, BUN, creatinine, serum albumin, AST, ALT, ALP, and TB)
 - Pharmacokinetic sampling for all subjects: pre-dose (Day 9 only)
 - Respiratory syncytial virus viremia
 - Local troponin testing (Day 17 only)
- Nasal samples (2 total, 1 from each nostril)
- 12-lead Pre-Dose ECG (Day 17 only)
- Urine or serum pregnancy test (for women unable to confirm menopause, hysterectomy and/or bilateral oophorectomy)
- Investigational medicinal product administration*
- Pharmacokinetic sampling for all subjects: 2 hours post-dose (± 15 min) (Day 9 only)
- Blood draw for serum creatinine at 2 hours (± 15 min) post-dose for PK subgroup subjects (Day 9 only)

- Assessment of AEs, concomitant medications, hospitalizations, re-hospitalizations, ICU admissions or utilization of ICU care > 24 hours, standard of care test results (ie, chest radiographs, microbiology, echocardiograms), mechanical ventilation (invasive and non-invasive of any duration), and supplemental O₂ use (≥ 2 L/min for >24 hours)

* Subjects will receive a single dose of 200 mg (four 50 mg tablets) of presatovir or matching placebo at Days 5, 9, 13, and 17. All IMP will be administered orally or via NG tube. The entire dose must be taken within 1 hour. Investigational medicinal product should be dispensed with gloves. Subjects will remain in the clinic for 30 minutes post-dose for observation. If vomiting occurs within 30 minutes after IMP administration and undissolved tablets are present in the vomitus, the subject should receive another dose. If another dose is administered, the subject should remain in the clinic for an additional 30 minutes post-dose for observation. Details of IMP administration are included in the Study Procedures Manual.

6.6. Visit 9: Day 22 (± 24 hours)

Visit 9 assessments must be performed in clinic or in hospital and should be performed in the following order and documented (also refer to [Appendix 2](#), Study Procedures Table):

- Vital Signs (body temperature, heart rate, respiratory rate, and blood pressure)
- O₂ saturation (on room air)
- Weight
- Blood draw for central laboratory analysis:
 - Safety Labs (hematology and serum chemistry to include to include WBC with differential, Hgb, platelets, BUN, creatinine, serum albumin, AST, ALT, ALP, and TB)
 - Pharmacokinetic sampling for all subjects
 - Respiratory syncytial virus viremia
- Nasal samples (2 total, 1 from each nostril)
- Obtain sample for local RSV testing* (refer to Section 6.11.11)
- Assessment of AEs, concomitant medications, hospitalizations, re-hospitalizations, ICU admissions or utilization of ICU care >24 hours, standard of care test results (ie, chest radiographs, microbiology, echocardiograms), mechanical ventilation (invasive and non-invasive of any duration), and supplemental O₂ use (≥ 2 L/min for > 24 hours)

PPD

6.7. Visit 10: End of Study/Day 28 (+3 days)

Visit 10 assessments must be performed in clinic or in hospital. The visit will occur no earlier than Day 28 and no later than Day 31. Visit 10 assessments should be performed in the following order and documented (also refer to [Appendix 2](#), Study Procedures Table):

- Vital Signs (body temperature, heart rate, respiratory rate, and blood pressure)
- O₂ saturation (on room air)
- Weight
- Blood draw for central and local laboratory analysis:
 - Safety Labs (hematology and serum chemistry to include to include WBC with differential, Hgb, platelets, BUN, creatinine, serum albumin, AST, ALT, ALP, and TB,)
 - Serum antibody titer to RSV
 - Respiratory syncytial virus viremia
 - Local troponin testing
- Nasal samples (2 total, 1 from each nostril)
- 12-lead ECG
- Assessment of AEs, concomitant medications, hospitalizations, re-hospitalizations, ICU admissions or utilization of ICU care > 24 hours , standard of care test results (ie, chest radiographs, microbiology, echocardiograms), mechanical ventilation (invasive and non-invasive of any duration), and supplemental O₂ use (≥ 2 L/min for > 24 hours)

6.8. Visits 11 – 14*: Days 35, 42, 49 and 56 (± 48 hours)

Visit 11 - 14 assessments may be performed in clinic, in hospital, or at the subject's home by the study coordinator or designee, or a home nursing vendor.

- Nasal samples (2 total, 1 from each nostril)
- Assessment of procedure-related AEs

PPD

6.9. Assessments for Premature Discontinuation from IMP dosing and Early Withdrawal

Reasons for premature discontinuation from IMP dosing or the study are outlined in Section 3.5.

6.9.1. Assessments for Premature Discontinuation from IMP Administration

If a subject prematurely discontinues IMP dosing, the subject will remain on study and will continue with all subsequent study visits and assessments through Visit 10, Day 28/End of Study Visit, with the exception of IMP administration.

6.9.2. Assessments for Early Termination/Withdrawal

Every attempt should be made to keep subjects in the study and to perform the required study-related and follow-up procedures (see Sections 6.2 through 6.7). If this is not possible or acceptable to the subject or investigator, the subject may be withdrawn from the study.

If a subject withdraws early from the study for any reason, every attempt should be made to bring the subject back to the clinic or hospital for the following early termination assessments:

- FLU-PRO questionnaire (only if the subject withdraws prior to Visit 6 [Day 9])
- Vital Signs (body temperature, heart rate, respiratory rate, and blood pressure)
- O₂ saturation (on room air)
- Weight
- Blood sample collection for central and local laboratory analysis:
 - Safety Labs (hematology and serum chemistry to include to include WBC with differential, Hgb, platelets, BUN, creatinine, serum albumin, AST, ALT, ALP, and TB)
 - Serum antibody titer to RSV
 - Respiratory syncytial virus viremia
 - Pharmacokinetic sampling (only if the subject withdrawals prior to Visit 9 [Day 22])
 - Local troponin testing
- Nasal samples (2 total, 1 from each nostril)
- 12-lead ECG
- Assessment of AEs, concomitant medications, hospitalizations, re-hospitalizations, ICU admissions or utilization of ICU care > 24 hours, standard of care test results (ie, chest radiographs, microbiology, echocardiograms), mechanical ventilation (invasive and non-invasive of any duration), and supplemental O₂ use (≥ 2 L/min for > 24 hours)

6.10. Assessments for Unscheduled Visits

Subjects who return to the clinic or hospital between scheduled study visits will have an unscheduled visit performed. The following procedures will be performed and documented at these visits:

- FLU-PRO Questionnaire, prior to all other study procedures (if unscheduled visit occurs prior to Visit 6 [Day 9])
- Vital signs, including O₂ saturation (on room air)
- Weight
- Collection of nasal samples (2 total, 1 from each nostril) for analysis at the central lab
- Assessment of AEs, concomitant medications, hospitalizations, re-hospitalizations, ICU admissions or utilization of ICU care > 24 hours, standard of care test results (ie, chest radiographs, microbiology, echocardiograms), mechanical ventilation (invasive and non-invasive of any duration), and supplemental O₂ use (≥ 2 L/min for > 24 hours)

6.11. Study Assessments

6.11.1. Nasal Samples, Virology, and Antibody Titer

Subjects with unknown RSV status may be tested for RSV at Screening using local laboratory methods. Further nasal sampling will be performed at all study visits PPD [REDACTED]).

Samples must be collected prior to dosing at all dosing visits. Two nasal samples will be obtained, 1 from each nostril, each time nasal sampling is performed. Samples will be stored and shipped to a central laboratory for testing.

In Japan only, 2 nasal swab samples will be collected at Screening; 1 will be processed for RSV locally, while the other will be sent to a central laboratory for analysis. To offset the collection of the additional nasal sample collected at Screening, only 1 sample will be collected for central laboratory analysis at the Baseline visit in Japan. All other visits in Japan will follow the same sampling schedule as the other global sites; 2 nasal swab samples collected, 1 from each nostril for shipment to and analysis by a central laboratory.

At any time during the study, if a bronchoscopy is planned for the same day as nasal sampling, nasal samples should be obtained, if possible, prior to application of any topical anesthetic (eg, lidocaine) in the nostrils. If it is not possible to collect nasal samples from both nares (eg, subject has an NG tube in place), 2 samples should be taken from the same naris and the tube for the second sample should be marked as "back-up." At Visit 9 (Day 22), PPD [REDACTED]

Nasal samples will be analyzed using RT-qPCR to determine RSV viral load, RSV sequencing to evaluate development of resistance (see Section 6.11.2), and a multiplex assay to identify co-infections. PPD

All nasal samples for central laboratory analysis will be collected, placed in individual tubes, and stored/shipped to the central laboratory as per instructions outlined in the Laboratory Manual.

Blood samples will be collected for RSV viremia evaluation (RT-qPCR) at Visits 2, 4, 6, 7, 8, 9, and 10 (Days 1, 5, 9, 13, 17, 22 and 28) prior to dosing, and RSV antibody titers at Visits 2 and 10 (Days 1 and 28). Samples will be processed, stored and shipped to the central laboratory as per instructions outlined in the Laboratory Manual.

6.11.2. Virology and Resistance Monitoring

To assess the potential for emergence of resistance to presatovir, population sequencing of the RSV F gene will be conducted on evaluable nasal swab samples collected from presatovir and placebo-treated RSV-infected subjects according to the Resistance Analysis Plan. In addition, all samples obtained from subjects who had quantifiable RSV RNA by RT-qPCR at the end of the study and PPD

Population sequencing of the RSV F gene will be conducted on evaluable nasal swab samples from all presatovir-treated RSV-infected subjects in this group. Any mutation in the F gene identified by population sequencing in presatovir-treated subjects relative to the pretreatment baseline sequence will be characterized phenotypically following their introduction into wild-type RSV using an established reverse genetics system. The susceptibility of the F mutant recombinants to presatovir will be assessed in cell-based antiviral susceptibility assays to determine whether each treatment-emergent mutation (TEM) confers reduced susceptibility to the compound.

6.11.3. FLU-PRO Questionnaire

The FLU-PRO questionnaire will be completed at Visits 2, 4, and 6 (Days 1, 5, and 9). The FLU-PRO should be administered prior to all other study procedures, however, if the FLU-PRO cannot be administered first it should be administered consistently at the required visits (ie, always after the same study procedure[s]). The FLU-PRO is currently being validated for evaluation of symptoms in patients who are infected with influenza. Due to the lack of validated tools for evaluation of RSV symptoms, and significant overlap between RSV symptoms and influenza symptoms, this tool will be used to assess change in RSV symptoms in this study. A copy of the FLU-PRO questionnaire may be found in the Study Procedures Manual.

6.11.4. Vital Signs

This assessment will include body temperature, heart rate, respiratory rate, and blood pressure. The subject is required to sit quietly for approximately 2 minutes prior to obtaining VS. Vital signs will be collected at all study visits, with the exception of Visits 3 and 5 if they are performed as home visits, PPD.

6.11.5. Oxygen Saturation

Oxygen saturation assessment will begin by first asking the subject to sit quietly for 1 minute. Oxygen saturation will be recorded while breathing room air, even if the subject is dependent on O₂ supplementation. If the subject is receiving supplemental O₂, the O₂ source must be removed for a period of 30 seconds prior to this assessment. This 30 second period may be conducted while the subject is sitting quietly. The O₂ saturation will be documented in the source documentation at regular intervals during a 2-minute testing period. Oxygen saturation evaluation will be considered complete when the 2-minute period has elapsed, or when the subject achieves a saturation of $\leq 88\%$, whichever is achieved first. The lowest O₂ saturation recorded over the 2-minute interval will be captured in the eCRF. Oxygen saturation will be collected at all study visits, with the exception of Visits 3 and 5 if they are performed as home visits, PPD .

Subjects requiring invasive mechanical ventilation will **not** have O₂ saturation measured while ventilated, and it should be recorded in the source documentation as not assessed and the reason should be documented. If it is determined by the investigator that it is unsafe to remove the subject's supplemental O₂ for assessment of O₂ saturation (eg, subject is on high-flow mask), then it should be recorded in the source documentation as not assessed and the reason should be documented.

6.11.6. Safety Labs

When available, the most recent laboratory values (obtained ≤ 6 days prior to Screening [Visit 1]) may be used for eligibility assessment, with the exception of RSV results and pregnancy testing. If an existing laboratory value is not available for eligibility assessment, the test will be performed using the local hospital laboratory. All blood samples will be collected pre-dose at all visits where IMP is administered.

Central laboratory testing of blood specimens for safety analysis will include WBC with differential, Hgb, platelets, BUN, creatinine, serum albumin, AST, ALT, ALP, and TB at Visits 2, 4, 6, 7, 8, 9, and 10 (Days 1, 5, 9, 13, 17, 22, and 28).

Any test showing an increase of serum ALT or AST $> 3 \times$ ULN or TB $> 2 \times$ ULN will be repeated within 48 to 72 hours for ALT, AST, ALP, and TB. If the repeat values are unchanged or are normalizing, monitoring will continue at weekly intervals until the results are acceptable or normalized. If any value has increased further, immediate close observation is required. If close monitoring is not possible, IMP will be discontinued.

Blood will also be drawn to monitor troponin levels pre-dose at Visits 2 and 8 (Days 1 and 17), and anytime at Visit 10 (Day 28). At each visit, the sample will be sent to the local lab at the clinical site for troponin analysis using the laboratory-based assay specific to the local trial site (eg, troponin I or T). Point-of-care "rapid" troponin tests are not acceptable for protocol-mandated troponin testing. The baseline troponin test must be pre-dose. However, troponin testing done for the purposes of patient care on the same day as a protocol-required test day may be used, provided the test is completed at the protocol-directed time and is a laboratory-based assay. Troponin results should be verified before the subject leaves the clinical site in case a troponin value is positive and further medical care is advised.

Blood specimens for serum creatinine will be collected 2 hours post-dose at Visits 2 and 6 (Days 1 and 9) from subjects participating in the PK subgroup only.

Urine or serum pregnancy tests will occur for all females of childbearing potential at Screening and at each dosing visit (Visits 2, 4, 6, 7, and 8) prior to administration of IMP.

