6.11.9.2. Clinical Data Collection for Cardiac Related Tests

Aside from the protocol-specified ECG and troponin collection, additional cardiac-related tests are not required for this study. However, throughout the study period (Baseline/Day 1 through Day 28/End of Study) if any cardiac-related testing is performed as part of standard clinical care, or as part of AE/SAE evaluation and/or follow-up, these results will be collected, including but not limited to the following:

- ECG tracings and reports of any ECG performed
- All troponin testing
- Other cardiac enzyme testing (eg, all CK, CK-MB, etc)
- Cardiac stress testing
- Echocardiographic imaging (resting and stress testing)
- Cardiac perfusions scans
- Cardiac MRIs
- Any additional procedure used to evaluate cardiac conditions

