- e Central laboratory testing: hematology and serum chemistry to include WBC with differential, Hgb, platelets, BUN, creatinine, serum albumin, AST, ALT, ALP, and TB
- f 2 samples total, 1 from each nostril – collected prior to dosing on dosing days.
- g For subjects in the PK subgroup only: Collected 1 (±15 min), 2 (±15 min), 4 (±30 min) and 6 hours (±30 min) post-dose
- h For all subjects: collected pre-dose on Day 5, pre-dose and 2 hours (±15 min) post-dose on Day 9, and anytime on Day 22

- i For subjects in the PK subgroup only: PK is collected anytime during Visit 3 and Visit 3 must occur in clinic.
- j For subjects in the PK subgroup only. Subjects not participating in the PK subgroup can have this visit completed at home by a home nursing vendor or by the study coordinator or designee.
- k For subjects in the PK subgroup only: Blood draw for serum creatinine 2 hours (\pm 15 min) post dose on Day 1 and Day 9 (Visit 2 and Visit 6)
- l Only for subjects who agree to the optional extended viral monitoring at the time of consent.
- m Only for subjects who agree to the optional extended viral monitoring at the time of consent and test positive (or inconclusive) for RSV at Visit 9 (Day 22)
- n Assessment of procedure-related AEs only, if home visit
- o Not required if home visit
- p Local troponin testing will be done pre-dose in accordance with the standard assay available and used at the site. Point-of-care “rapid” troponin tests are not acceptable for protocol-mandated troponin testing.
- q Visit 3: Day 3 is an optional study visit for subjects not participating in the PK subgroup.
- r For Japan sites only, 2 nasal swab samples will be obtained at Screening, 1 for local RSV testing and 1 for testing at the central laboratory. At Baseline, only 1 sample will be obtained for central laboratory testing.
- s Subjects who were not tested for RSV as standard of care may consent to the study and be tested subjects for RSV during the Screening visit.

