7.2.1.1. Troponin

Troponin will be collected at the visits pre-specified in the protocol: Day 1, Day 17 and Day 28 (End of study). A shift table of troponin results at postbaseline visit including those obtained for the purposes of standard of care compared with baseline values will be presented by treatment group using the following categories: normal, abnormal, or missing. The number and percentage of subjects in each cross-classification group of the shift table will be presented. Subjects with a missing value at baseline or postbaseline will not be included in the denominator for percentage calculation. No formal statistical testing is planned.

If multiple troponin results exist for one visit due to multiple troponin assay tests performed, the results obtained from Troponin I test will be used for the analysis.

All troponin results, including those not required by the protocol (see protocol Section 6.11.9.2), will be presented in the subject listings.

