15.11.6.1.5	Hematology Test: Monocytes (%) and Change from Baseline	Safety Analysis Set
15.11.6.1.6	Hematology Test: Neutrophils ($\times 10^3/\mu\text{L}$) and Change from Baseline	Safety Analysis Set
15.11.6.1.7	Hematology Test: Neutrophils (%) and Change from Baseline	Safety Analysis Set
15.11.6.1.8	Hematology Test: Platelets ($\times 10^3/\mu\text{L}$) and Change from Baseline	Safety Analysis Set
15.11.6.1.9	Hematology Test: Leukocytes ($\times 10^3/\mu\text{L}$) and Change from Baseline	Safety Analysis Set
15.11.6.2.1	Chemistry Test: ALT (U/L) and Change from Baseline	Safety Analysis Set
15.11.6.2.2	Chemistry Test: AST (U/L) and Change from Baseline	Safety Analysis Set
15.11.6.2.3	Chemistry Test: ALP (SGPT) (U/L) and Change from Baseline	Safety Analysis Set
15.11.6.2.4	Chemistry Test: Total Bilirubin (mg/dL) and Change from Baseline	Safety Analysis Set
15.11.6.2.5	Chemistry Test: Blood Urea Nitrogen (mg/dL) and Change from Baseline	Safety Analysis Set
15.11.6.2.6	Chemistry Test: Creatinine (mg/dL) and Change from Baseline	Safety Analysis Set
15.11.6.2.7	Chemistry Test: Creatinine Clearance (mL/min) and Change from Baseline	Safety Analysis Set
15.11.6.2.8	Chemistry Test: Albumin (g/dL) and Change from Baseline	Safety Analysis Set
15.11.6.2.9	Timed Serum Creatinine (mg/dL) and Change from Baseline by Hourly Timepoint	Safety Analysis Set
15.11.6.4.1.1	Treatment Emergent Laboratory Abnormalities	Safety Analysis Set
15.11.6.4.1.2	Treatment Emergent Laboratory Abnormalities by Age Group (<65 Years or ≥ 65 Years)	Safety Analysis Set
15.11.6.4.1.3	Treatment Emergent Laboratory Abnormalities by Sex (Male or Female)	Safety Analysis Set

Table Number	Title	Analysis Set
15.11.6.4.1.4	Treatment Emergent Laboratory Abnormalities by Race (White or Others)	Safety Analysis Set
15.11.6.4.2	Treatment Emergent Grade 3 or 4 Laboratory Abnormalities	Safety Analysis Set
15.11.6.4.3	Treatment Emergent Marked Laboratory Abnormalities	Safety Analysis Set
15.11.6.5	Liver-Related Laboratory Abnormalities	Safety Analysis Set
15.11.6.6.1	Shift in Troponin Results	Safety Analysis Set
15.11.6.6.2	Subjects with Abnormal Troponin Results at Postbaseline through Day 28	Safety Analysis Set
15.11.7.1.1	Vital Signs: Diastolic Blood Pressure (mmHg) and Change from Baseline	Safety Analysis Set
15.11.7.1.2	Vital Signs: Systolic Blood Pressure (mmHg) and Change from Baseline	Safety Analysis Set
15.11.7.1.3	Vital Signs: Pulse (beats per minute) and Change from Baseline	Safety Analysis Set

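### The two planned by-arm troponin tables cannot show a rise from an abnormal baseline, and at visits with more than one assay the Troponin I rule ignores which assay gave the baseline

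*Protocol*

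**What the plan says.** Protocol 6.11.6 (Safety Labs) schedules troponin before dosing on Days 1 and 17, and at any time on Day 28. The sample goes to the site's own laboratory and is tested "using the laboratory-based assay specific to the local trial site (eg, troponin I or T". The footnote in Protocol Appendix 2 likewise has testing done "in accordance with the standard assay available and used at the site". A same-day patient-care result may stand in for the protocol test, "provided the test is completed at the protocol-directed time and is a laboratory-based assay"; the assay type need not match. Protocol 6.11.9.2 also collects "All troponin testing" done in standard care or for adverse event work-up.

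SAP 7.2.1.1 plans a shift table against baseline, with standard-of-care results included after baseline, which "will be presented by treatment group using the following categories: normal, abnormal, or missing". If several assays were run at one visit, "the results obtained from Troponin I test will be used for the analysis". Every troponin result goes into a by-subject listing (Listing 16.2.8.1.8).

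SAP 12.1 lists two troponin tables: 15.11.6.6.1, the shift table, and 15.11.6.6.2, "Subjects with Abnormal Troponin Results at Postbaseline through Day 28". SAP 7.2.1, the parent section, promises baseline values, post-baseline values and change from baseline for each laboratory test in the protocol. No table or figure of that kind is listed for troponin.

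**The concern.** Troponin and the ECG are the two cardiac tests that the protocol schedules. A by-arm comparison of troponin is useful only if it can register worsening. Two features limit it.

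First, two categories carry no magnitude. A subject abnormal on Day 1 stays in the same cell however far the value rises. No entry criterion in Protocol 4.2 or 4.3 names troponin, so such subjects can be enrolled.

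Second, the rule for several assays at one visit depends neither on the baseline assay nor on which result is abnormal. It can pair unlike assays when a like pair exists, and it can set aside the only abnormal result at that visit.

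What is at stake is the completeness of a descriptive safety comparison. No efficacy result and no formal test depends on it.

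**Working it through.** The plan states no figure that could be reproduced, so the check sets the sections side by side and applies the SAP rule to constructed cases.

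**Does another by-arm table show magnitude?**
- SAP 7.2.1 would supply one if read literally, but SAP 12.1 and 12.2 list no numeric troponin table or figure.
- The graded-abnormality tables (15.11.6.4.1.1 to 15.11.6.4.3) rest on the scale in Protocol Appendix 4, which has no troponin row.
- The adverse event tables cover it only in part. Under Protocol 7.1.3, laboratory abnormalities without clinical significance are not recorded as adverse events.
- Within the listed output, a rise from an abnormal baseline therefore appears only in the listing.

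**What does the Troponin I rule do?**

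| Day 1 | Day 17 | Result used after baseline | Shown in 15.11.6.6.1 | What is lost |
|---|---|---|---|---|
| T abnormal | T abnormal, much higher | T (only assay) | abnormal to abnormal | the rise |
| T normal | T abnormal, I normal | I | normal to normal | the abnormal T and the matching T pair |
| T normal | T normal, I abnormal | I | normal to abnormal | the comparison is T with I although a T pair exists |
| I and T | T only | T, against I at Day 1 | I compared with T | the matching T pair |
| one assay | same assay | that assay | like with like | nothing from this rule |

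Row 1 follows from the two categories. Rows 2 to 4 follow from the assay rule and arise only when some visit has both assays. In row 2 the abnormal T also leaves Table 15.11.6.6.2, if the words of SAP 7.2.1.1 on which result is used govern both tables.

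The rule also differs from the SAP's own convention. For post-baseline categorical records on the same day that share a time or have none, SAP 3.8.4 takes the worst category. Row 2 takes the better one.

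**How many subjects could be affected by row 1?** The documents give no rate of abnormal baseline troponin, so this is an assumed range.
- Enrolled: 189 (SAP 1.3), randomized 1:1, so 189 / 2 = 94.5 per arm.
- At 10% abnormal on Day 1: 0.10 × 94.5 = 9.45, about 9 per arm.
- At 40%: 0.40 × 94.5 = 37.8, about 38 per arm.

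These subjects cannot show an upward shift. For rows 2 to 4 the documents give no basis for any frequency.

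**The case against.** Several points on the other side stand.

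- The Troponin I rule is narrow. The default is the site's own assay, so a site that uses one assay throughout gives like-with-like shifts. A mismatch needs a site that runs both assays, a change of assay, or an added patient-care test.
- Local assays do not by themselves invalidate a normal/abnormal table. Classifying each result against its own laboratory's range is an ordinary way to pool assays, although SAP 7.2.1.1 does not state the reference used.
- Protocol 8.6.3 speaks of selected laboratory data, so the protocol does not compel a numeric troponin table. The mismatch lies between SAP 7.2.1 and the SAP's own table list.
- Other safeguards exist. All troponin results are listed, sites should check results before the subject leaves, cardiac adverse events of interest are tabulated by arm (Tables 15.11.2.4 and 15.11.4.4), and the DMC reviews all available safety data. None of these compares troponin magnitude between arms in the planned output.

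A reader might infer three stronger things, and the documents support none of them.

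- *That a rise from an abnormal baseline is invisible.* It is in the listing; it is missing only from the by-arm tables.
- *That a difference between arms would be lost altogether.* The shift table separates subjects by baseline status. Suppose 30% of 95 per arm are abnormal at baseline and true rises occur in 10% versus 2% regardless of baseline. The baseline-normal row then has 0.70 × 95 = 66.5 subjects per arm and shows 6.65 / 66.5 = 10% versus 1.33 / 66.5 = 2%, so the contrast survives there. Table 15.11.6.6.2 could dilute it, but the SAP does not say whether that table counts subjects already abnormal at baseline.
- *That the troponin section answers an FDA cardiac monitoring requirement.* The SAP revision log (Section 11) gives that reason for Section 7.1.7, the cardiac adverse events. Its troponin entry cites only detail and clarification.

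**Conclusion.** The point holds in limited form. The two listed by-arm troponin tables cannot show worsening in subjects who start abnormal, and SAP 7.2.1 promises numeric output that the table list omits. At visits with more than one assay, the Troponin I rule can compare unlike assays and can drop an abnormal T.

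The first limitation affects only baseline-abnormal subjects: about 9 to 38 per arm on the assumed 10% to 40%. The second affects only subjects with a multi-assay visit, in a number that the documents do not allow to be estimated. The effect on Table 15.11.6.6.2 also assumes that the rule in SAP 7.2.1.1 governs that table, which the text does not define.

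This is a minor improvement to descriptive safety output, worth making because it is cheap. It is not a fault in the trial's safety monitoring as a whole.

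**What to change.** Amend SAP 7.2.1.1 in three places.

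1. **Shift table (15.11.6.6.1).** Replace the Troponin I default with the post-baseline result from the same assay as baseline, where one exists. If Day 1 has both assays, pair like with like, and state in advance which pair is used when both are available. Flag subjects with no matching assay.
2. **Post-baseline table (15.11.6.6.2).** Count a subject as abnormal if any assay is abnormal after baseline, and present the table by baseline status. This table need not be restricted to matched assays, because it makes no within-subject comparison of values.
3. **New by-arm summary of change.** Within assay, give the multiple of the local upper limit of normal or the fold change from baseline, with baseline-abnormal subjects shown separately. This also reconciles SAP 7.2.1 with the table list, and it avoids pooling raw I and T concentrations.

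The cost is SAP wording, programming and one added table, with no new procedure for subjects. Assay type and the local upper limit must be available for each result. A few subjects without a matching assay become non-evaluable for the shift and should be counted as such.
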